14.4. Type I error rate

The Type I error rate is 5% and all tests are two-tailed.

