14.5.4. Power

The assumptions underlying the power analysis for MET-weighted minutes of MVPA are summarized in Table 14.1.

- The mean and standard deviation for MET-weighted minutes of MVPA are taken from the variance components substudy of 8th grade girls (n=426) selected to represent 12 schools from the six Field Centers. Both are based on a cutpoint of 1500 CSA counts per half-minute to define MVPA, a figure drawn from the findings of the CSA calibration substudy.
- As noted above, the Type I error rate for the primary analysis is 5% and twotailed.
- Given 60 girls per school invited to the baseline survey, we conservatively
 estimate the overtime correlation among schools at zero (the correlation among
 measures taken on the same schools two years apart). We make no provision
 for overtime correlation among the girls (the correlation among measures taken
 on the same girls two years apart), due to our plan to ignore any overlap in the
 6th and 8th grade samples.
- We plan to randomize 18 schools to each of two conditions.
- We assume each Field Center will average 60 girls per school selected for invitation to the baseline survey and 120 girls per school selected for invitation to the follow-up survey. Schools with fewer girls available for CSA measurements may participate in TAAG so long as there is a minimum of 90 girls who are eligible to be selected for invitation to each survey and so long as each Field Center averages 60 girls per school at the baseline survey and 120 girls per school at the follow-up survey.
- We anticipate that girls enrolled in the intervention schools during 7th and 8th grade will display an intervention effect of 15.6 more MET-weighted minutes of MVPA than their counterparts in the control schools; this effect is equivalent to 10% of the mean MET-weighted minutes of MVPA and to a 50% reduction in the decline anticipated between the 6th and 8th grades. We anticipate that girls enrolled in the intervention schools only in the 8th grade will display an intervention effect of 9.4 more MET-weighted minutes of MVPA and to a 30% reduction in the decline anticipated between the 6th and 8th grade soft MVPA, this effect is equivalent to 6% of the mean MET-weighted minutes of MVPA and to a 30% reduction in the decline anticipated between the 6th and 8th grades.
- Our eligibility criteria are designed to limit the two-year attrition to 36%.

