- The observed value of the school-level ICC for MET-weighted minutes of MVPA is 0.000, based on an analysis of the variance components substudy data consistent with that proposed above for the primary analysis. We view that estimate as optimistic and prefer to be cautious, given that we had a small sample of schools in the variance components substudy, thereby limiting the precision of our estimate. Separate analyses suggest a 50% probability that the true value is below 0.003 given an observed value of 0.000, and so we propose 0.003 as our realistic estimate of this Intraclass Correlation. Prior experience with Intraclass Correlations in other school based studies suggests a value of 0.01 as a conservative estimate, and we note that there is a 62% probability that the true value is below 0.01 given an observed value of 0.000. With these considerations in mind, we used these three values to perform the power analyses summarized in Table 14.2.

Table 14.1. Assumptions Underlying the Power Analysisfor MET-Weighted Minutes of MVPA

Mean MET-weighted minutes of MVPA, based on 1500	156.4 MET minutes
cpm	
SD MET-weighted minutes of MVPA, based on 1500	94.9
cpm	
Two-tailed Type I Error Rate	5%
Over-time correlation among schools	none
Over-time correlation among girls	none
Schools per condition	18
Girls per school selected for CSA measurement at	Average 120, Minimum 90
posttest	
Intervention effect	
for girls enrolled in intervention schools in 7 th and 8 th	15.6 MET min (10% of
grade	mean)
for girls enrolled in intervention schools only in 8 th	9.4 MET min (6% of mean)
grade	
Attrition rate over two years	36%
Refusal rate at follow-up for CSA measurements	20%
CSA measurement schedule	
days per girl	6 24-hour days
weeks per school	3
Imputation of occasionally missing CSA data	EM algorithm
Imputation for non-ignorable refusals	none
School-level Intraclass Correlation	
observed estimate	0.000
realistic estimate	0.003
conservative estimate	0.010

Tables 14.2 summarizes power for TAAG based on these assumptions. These results indicate that even if the Intraclass Correlation is as high as 0.01, if we invite 120 girls from each school to participate in the follow-up survey, and no more than 20% of that sample refuse to provide CSA data, we have 89% power for the projected intervention effect, given the assumptions noted in Table 1.

ICC	Girls/Sc	hool Invite	d to Partic	cipate at F	ollow-up
100	90	105	120	135	150
0.010	81%	85%	87%	89%	90%
0.003	92%	95%	97%	98%	98%

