 $MVPA = \text{condition} + MVPA_{\text{baseline}} + \text{fieldcenter} + \text{school}(\text{condition} \times \text{fieldcenter}) + \text{stratum} + \text{stratum} \times \text{school}(\text{condition} \times \text{fieldcenter})$ (7)

The expected mean squares for this model are shown below:

The degrees of freedom total 72 because there are 72 follow-up school x stratum means. The degrees of freedom that are otherwise used by the condition x Field Center interaction fall to the school term, bringing the total for that term to 29. The degrees of freedom that are otherwise used by the stratum x Field Center and condition x stratum x Field Center interactions fall to the stratum x school term, bringing the total for that term to 33.

In this analysis, the term of interest is the stratum x condition interaction, as it reflects any differential intervention effect between the strata. It is tested against the stratum x school interaction, with 1 and 33 degrees of freedom. The intervention effect is estimated as the net difference among four adjusted posttest means: upper(I-C)-lower(I-C), where upper and lower refer to the two strata.

(6)

Source	df		E(MS)	MS
Intercept		= 1		
Condition	c-1	= 1	$s\sigma_{g:cf}^2 + fsg\sigma_c^2$	MS _c
MVPA _{baseline}		= 1		
FieldCenter	f -1	= 5	$s\sigma_{g:cf}^2 + sgc\sigma_f^2$	MS_{f}
School	cf(g-1) = 24		$s\sigma_{g:cf}^2$	MSg:cf
	+(c-1)(f-1) = 5		from condition x field center	
		= 29		
Stratum	s – 1	= 1	$\sigma_{sg:cf}^2 + fgc\sigma_s^2$	MSs
Condition × Stratum	(s-1)(c-1)	= 1	$\sigma_{sg:cf}^2 + fg\sigma_{sc}^2$	MS _{sc}
$Stratum \times School$	(s-1)cf(g-1) = 24		$\sigma^2_{ m sg:cf}$	MS _{sg:cf}
	+(s-1)(f-1) = 5		from stratum x field center	
	+(s-1)(c-1)(f-1) = 5		from condition x stratum x fie	eld center
	-1	= 33	correction for school - level co	ovariate
Total	(0)	= 72		
	(8)			

Given the same assumptions as for the primary analysis, and with the additional assumption that stratification reduces the girl and school-level variances by 10%, we calculate the power for the interaction effect in this stratified version of the primary analysis applied to the nested cross-sectional design. Table 1 presents power for an interaction effect of 6.67% in an analysis of girl-level effect modification.

Table 1. Power projected for girl-level effect modification					
ICC	Girls/School Invited to Participate at Follow-up				
	90	105	120	135	150
0.010	30%	32%	34%	36%	37%
0.003	40%	44%	48%	52%	55%
0.000	47%	53%	59%	64%	69%

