Under the original plan, we expected to have 49 girls per school available in the cohort if we selected 120 girls per school at baseline given a two-year attrition rate of 36% and annual refusal rates of 20%. That figure is reduced to 25 girls per school given only 60 girls per school at baseline. With 36 schools, that still provides 900 girls in the cohort, and the degrees of freedom for those analyses are unchanged, as they are still based on 36 schools. Power calculations for an intervention effect on a hypothesized mediator indicate that there is 80% power for an effect of 0.21 sd units and 90% power available for an effect of 0.25 sd units. An effect size of 0.25 sd units is widely considered to be small (Cohen, 1988). In contrast, our hypothesized intervention effect on MET-weighted minutes of MVPA of 10% represents an effect size of 14.5/86=0.17 sd units, which is quite small. This is why, the power for the mediation analysis is reasonable even with a reduced baseline sample.

Power for moderation is diminished by reducing the size of the baseline sample, but is already poor, so we don't do too much harm by reducing it further.

A.4.7. Power Calculations for PWC₁₇₀

Cardiovascular fitness will be assessed by the Physical Work Capacity 170 (PWC₁₇₀) cycle ergometer test. For the PWC₁₇₀ test, the outcome measure will be the predicted power output based on a two-stage required to elicit a heart rate of 170 beats/min. We will express, PWC₁₇₀ as kilogram-meters per minute per kilogram lean body weight (kg-m/min/kg). The estimates used in the power calculations below were from studies that controlled for total weight, rather than more precise measures of lean body weight that we will use. Therefore, the estimates shown here may be conservative.

Using a cross-sectional design, we will model the 36 school-level fitness means at the end of 8th grade as a function of treatment condition, site, and school. Power calculations were performed for a 2-sided type I error rate of 0.05. We assumed a mean and standard deviation for PWC₁₇₀ of 11 ± 2.7, an ICC estimate of 0.01. The following table shows the power to detect a 5% or 6% difference in fitness at 8th grade as a function of the number of girls invited to participate in the fitness measure in each school, with the expectation that 80% will participate.

POWER FOR PWC ₁₇₀ - 36 Schools				
Girls Invited	Intervention effect			
Per School	5% 6%			
60	0.88	0.96		
50	0.84	0.94		
40	0.78	0.91		
30	0.68	0.83		

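### Appendix 4, Table 1 charges the full school-level ICC to each stratum mean of a within-school contrast, while the stratum x school component that the test uses has no stated value; it also does not halve the girls per stratum

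*Protocol*

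**What the plan says.** Protocol Appendix 4, A.4.5.1.1, deals with effect modification by an immutable girl-level factor such as age. Girls are split at the grade-specific study-wide median, so each school contributes girls to both strata and stratum is crossed with school. The second stage uses 72 follow-up school x stratum means. In the expected mean squares table (8) the Condition x Stratum line contains the stratum x school variance and its own effect. The school variance appears only in the Condition, Field Center and School lines. The text confirms the error term: "It is tested against the stratum x school interaction, with 1 and 33 degrees of freedom".

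Power is then calculated on the assumptions of the primary analysis plus "the additional assumption that stratification reduces the girl and school-level variances by 10" percent. The protocol adds: "Table 1 presents power for an interaction effect of 6.67% in an analysis of girl-level effect modification". The rows of Table 1 are the three school-level ICC values of Table 14.1 (0.010, 0.003, 0.000). At 120 girls invited it prints 34%, 48% and 59%.

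A.4.5 also states that, with girl-level stratification, the number of girls per condition x stratum x Field Center cell is half of what the primary analysis has per condition x Field Center.

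**The concern.** The contrast of interest is upper(I-C) minus lower(I-C), formed from two strata inside the same schools. A school effect common to all girls of a school drops out of it. What remains is girl-level sampling error plus any stratum x school variation. Table 1 gives that variation no value of its own and uses the school-level ICC as its row variable.

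If the ICC is charged in full to each stratum mean, the table describes a design in which the two strata come from different schools. That is the situation of Table 2 (school-level moderators), not of Table 1. A reader would take from Table 1 that power for girl-level moderation depends heavily on the school ICC, with a spread of 25 points at 120 invited. A reader would also conclude that measuring more girls gains little at ICC 0.010, where power rises only from 30% to 37% between 90 and 150 invited.

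**Working it through.** **Inputs**
- Test: "The Type I error rate is 5% and all tests are two-tailed" (14.4), with 33 error degrees of freedom (A.4.5.1.1).
- Schools: "We plan to randomize 18 schools to each of two conditions" (14.5.4).
- SD: "SD MET-weighted minutes of MVPA, based on 1500" cpm is 94.9 (Table 14.1). With the 10% variance reduction, σ² = 0.9 × 94.9² = 8105.
- Main effect: girls exposed in both grades "will display an intervention effect of 15.6 more MET-weighted minutes of MVPA than their counterparts in the control schools", and those exposed in 8th grade only show 9.4 (14.5.4). I assume that half of the 36% attrition figure gets the partial dose: 0.82 × 15.6 + 0.18 × 9.4 = 14.48. The protocol does not state this weighting, but A.4.6.2 says the 10% effect "represents an effect size of 14.5/86=0.17 sd units", which agrees.
- Interaction effect: 6.67% against 10%, so 2/3 × 14.48 = 9.66 MET-minutes.
- Girls measured: 80% of those invited, so 96 at 120 invited.

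**Step 1. Check of the inputs.** A noncentral t calculation with effect 14.48, 28 df and variance 2 × 94.9² × [ICC + (1−ICC)/m]/18, m = 0.8 × invited, reproduces all 15 cells of Table 14.2 within 0.8 points.

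**Step 2. Reproducing Table 1.** Charge the full ICC to each of the four means and do not halve the girls:

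Var = 4σ²[ICC + (1−ICC)/m]/18, with m = 96 at 120 invited.

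| ICC | SE | Power | Printed |
|---|---|---|---|
| 0.010 | 6.05 | 34.1% | 34% |
| 0.003 | 4.91 | 48.0% | 48% |
| 0.000 | 4.33 | 58.1% | 59% |

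All 15 cells agree within 1.3 points. Halving m with the ICC in each mean misses by up to 29 points. The same variance with 9 schools per cell and 26 df reproduces Table 2 within 1.3 points, so Table 1 uses the form suited to strata made of different schools.

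**Step 3. The contrast as specified.** Let ρ be the correlation of the school effects between the two strata of a school:

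Var = 4σ²[ICC(1−ρ) + (1−ICC)/m]/18.

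The part ICC(1−ρ) is the stratum x school contribution. At ρ = 1 the school effect is shared and cancels; at ρ = 0 the formula of Step 2 returns. The protocol gives no ρ, so 0 to 1 is an assumed range.

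Power at 120 invited:

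| ICC | m = 96, ρ = 0 (as printed) | m = 96, ρ = 1 | m = 48, ρ = 0 | m = 48, ρ = 1 |
|---|---|---|---|---|
| 0.010 | 34.1% | 58.5% | 24.3% | 33.7% |
| 0.003 | 48.0% | 58.2% | 29.9% | 33.5% |
| 0.000 | 58.1% | 58.1% | 33.4% | 33.4% |

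With a shared school effect the three ICC rows differ by less than 0.5 point, whichever girl count is used.

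**Step 4. Across the columns.** With girls halved and a zero stratum x school component, power for 90/105/120/135/150 invited is about 26/30/33/37/40%. The gain from 90 to 150 is then about 14 points, against the printed 7 at ICC 0.010.

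**The case against.** The strongest reply is that the error term is itself a between-school variance. The plan keeps stratum x school as a random effect (14.6.3 and A.4.5.1.1) and nothing sets it to zero. If the school effects in the two strata are independent, each with variance ICC × σ², charging the ICC to each mean is correct. This stands in part. A reader might infer that the ICC rows are simply spurious or that no between-school variance belongs in this test; the documents do not support that. They do leave the independence assumption unstated, and it sits badly with the claim to share the primary analysis's assumptions. Averaging two independent effects halves their variance, so the overall school ICC would be about half the row label.

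It can also be said that the symbols in table (8) are variances of second-stage means, so the missing school line does not by itself fix which ICC value enters. That is fair. The cancellation follows from crossing stratum with school, and table (8) is consistent with it.

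A second tempting reading is that true power at ICC 0.010 is 58% rather than 34%. That figure needs 96 girls in each stratum, which A.4.5 contradicts.

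Finally, little depends on the table. Section 14.6.3 presents effect modification as an aid to understanding and not as a test of prior hypotheses, A.4.6.2 already calls moderation power poor, and the sample size rests on Table 14.2. This stands and limits the severity.

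**Conclusion.** The point holds as a minor one. Table 1 uses the school-level ICC in place of a stratum x school component that is never given a value, and its 34%/48%/59% spread holds only at the unstated extreme ρ = 0. The same table does not halve the girls per stratum.

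With both put right, power at 120 invited and ICC 0.010 lies between about 24% (all of the ICC stratum-specific) and about 34% (none of it). It is about 33% with no school component at all. The two faults pull in opposite directions: charging the ICC in full lowers the printed power, and failing to halve the girls raises it. In the 0.010 row they roughly offset each other, so the 34% cell is close to the zero-component answer by coincidence. The 48% and 59% cells are too high, mainly because of the girl count.

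These figures rest on the inferred effect of 14.48 MET-minutes, an even split of girls within each school, and ρ between 0 and 1. The primary analysis is unaffected, and the protocol's own conclusion that moderation power is poor is unchanged.

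**What to change.** Recompute Table 1 from the error term that the test uses: girl variance divided by the halved number of girls per stratum per school (48 at 120 invited), plus an explicit stratum x school component. Show that component at zero and at an upper value, or use an estimate from the 6th-grade survey, and label the rows by it instead of by the school-level ICC. State in one sentence what is assumed about school effects across the two strata. Table 2 needs no change on this account, since its strata really are different schools. The cost is the recalculation of one table and a line of text; design, sample size and primary analysis stay as they are.
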